12.4.1.3 Primary Efficacy Analysis

12.4.1.3.1 Epworth Sleepiness Scale for Children and Adolescents (ESS-CHAD) [parent/caregiver version]

The primary endpoint is change in mean ESS-CHAD (parent/caregiver version) score from Baseline to Week 11 (Visit 5).

The parent/caregiver version of the ESS-CHAD is an Likert rating scale where parents/caregivers rate their child's/care recipient's likelihood of falling asleep over the past month while engaging in eight different activities. If the patient has not engaged in an activity, the parent/caregiver is asked to imagine how the activity would have affected the patient. Responses are rated on a scale where

. A global score, which represents the sum of responses across all eight items, ranges from ; higher scores correspond to greater daytime sleepiness. If one or more item-scores are missing, the score will be missing.

The score can be interpreted as:

12.4.1.3.2 Estimand

The primary efficacy endpoint is defined as the change in mean ESS-CHAD (parent/caregiver version) score from Baseline to Week 11 (Visit 5) for high dose pitolisant compared with placebo.

The target population is all patients in the mITT population with PWS as defined by the inclusion/exclusion criteria.

A treatment policy strategy will be used to address intercurrent events. No special data handling will be used for patients who initiate concomitant medications, have intermittent missing data, or discontinue study medication (even if they report data following discontinuation of study medication). No explicit imputation of missing data will be performed; the MMRM approach assumes data are missing at random and will provide unbiased results if this is the case. Sensitivity analyses will explore the results under different analysis assumptions.

12.4.1.3.3 Analysis

A descriptive summary (mean, SD, median, minimum, maximum) of the mean ESS-CHAD (parent/caregiver version) score (absolute values and change from Baseline) will be reported by treatment group and for the active groups combined. Early Termination visits will be summarized under Visit 3, Visit 4 or Visit 5 (depending on which visit they are closest to, per section 9.2) regardless of the discontinuation reason.

Frequency count and percentage of the ESS-CHAD (parent/caregiver version) score category (state and percentage of the ESS-CHAD (parent/caregiver version) responder (improvement of points from Baseline or a score which is less or equal to will be tabulated by treatment group and active groups combined. Percentages will be based on the number of patients with non-missing ESS-CHAD (parent/caregiver version) at Baseline and at each post-baseline visit. Patients with a score at Baseline which is less or equals will not be included in the summary.

No explicit imputation will be performed for the primary analysis; however, the MMRM model will yield unbiased results under the assumption that data are missing at random.

The change from Baseline will be analyzed in an MMRM analysis. Fixed effects will be included for treatment, Baseline value, visit and a term for the interaction between treatment and visit. An unstructured covariance structure will be utilized; Kenward-Rogers degrees of freedom will be used.

In the case of convergence issues, the following steps will be implemented (in the order listed) until convergence is reached.

- 1. The Fisher scoring algorithm will be used to start the first iteration to obtain the initial values of the covariate parameters (via the SCORING option of the PROC MIXED statement).
- 2. The no-diagonal factor analytic structure (via the TYPE=FA0(T) option of the REPEATED statement, where T is the total number of time points), which effectively performs the Cholesky decomposition of the covariance matrix and is numerically more stable.
- 3. The successive univariate regression (Lu 2010) will be implemented.
- 4. Covariance matrix of ARH(1) (Heterogeneous auto-regressive 1), and CS (compound symmetry) with the sandwich variance estimator will be used in that order (for the sandwich variance estimator Kenward-Rogers degrees of freedom will be replaced by the EMPIRICAL option).

LS means, standard errors, and the LS mean differences (each treatment versus placebo and the pooled active groups versus placebo) will be reported. All estimates will be generated from a single model, i.e., the pooled estimates will be created via model contrasts. The primary comparison of interest is the difference in the high dose group versus placebo at Visit 5.

Examples of SAS code are provided in Appendix 4.

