- ^a In the event that a portion of the Screening Visit is conducted remotely, specific procedures for both the Screening Visit and Baseline Visit will be conducted as detailed in Section 6.6.
- The 3-week Titration Period for the Double-Blind Treatment Phase will be from Days 1 to 21 (±3 days). Patients should take their first dose of study drug on the day after the Baseline Visit (Day 1), and study drug dose will be titrated on Day 8 and again on Day 15 (as appropriate based on randomized stable dose, Table 7); all patients will be at their randomized stable dose of study drug by Day 15. Patients and/or their caregivers will receive TCs on Days 8 and 15 (±3 days) to assess for AEs and concomitant medication use, complete the C-SSRS, and review/confirm titration of study drug.
- ^c The 8-week Stable Dose Period in the Double-Blind Treatment Phase will be from Days 22 to 77 (±3 days); patients will take their last dose of blinded treatment on Day 77 ±3 days; study drug compliance will be monitored at TCs and study visits as detailed in Section 5.5.
- d In the event that Visit 3 and/or Visit 4 are conducted remotely, specific procedures will be conducted as detailed in Section 6.6.1.2.
- e Visit 5 (Day 77 ±3 days) is the EOT visit for the Double-Blind Treatment Phase. Eligible patients who enter the optional OLE Phase will be dispensed open-label pitolisant at this visit (Section 5.2.2); eligibility criteria must be confirmed before a patient can participate in the OLE Phase.
- f Patients who prematurely discontinue study drug are required to complete the ET Visit. Procedures to be performed are the same as for the EOT Visit (Section 7.3.3). Reasons for discontinuation must be recorded.
- g Patients who do not enter the optional OLE Phase will receive Safety Follow-up TCs from the study site 15 (±3 days) and 30 days (+3 days) after their final dose of blinded treatment to assess for AEs (including inquiries regarding signs and symptoms of arrhythmia, any other cardiac manifestations [e.g., syncope], and psychiatric events [e.g., suicidality, compulsive behavior, anxiety]) and concomitant medication use.
- h Unscheduled visits and assessments may be conducted by telephone or at an on-site study visit and should be performed if clinically indicated in the opinion of the Investigator (Section 7.6).
- i Serum pregnancy test is to be performed at Screening and a urine pregnancy test is to be performed at all other visits, as indicated.

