9.2. Determination of Sample Size

The sample size is 60 patients (20 in the lower dose pitolisant group, 20 in the higher dose pitolisant group, and 20 in the placebo group). Prior research suggests that the ESS-CHAD SD falls between 5 to 6; at the lower end of this range, the study would be powered at 80% to detect a difference of 3.9 between the pooled pitolisant groups and placebo group. However, as a proof of concept, statistical separation is not a strict objective of the trial. The proposed sample size will yield a 95% confidence interval of ± 2.7 with an SD of 5 and ± 3.2 with an SD of 6; this will give sufficient precision to inform future studies.

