9.2.1 Visit Window

The visit window and PK draw window appear in Table 5 and Table 6, respectively. For the Double-Blind Treatment Phase, unless otherwise stated, the endpoints will be analyzed and reported using the analysis visits as determined by the windowing. For the OLE Phase, unless otherwise stated, the nominal visit will be used.

During the Double-Blind Treatment Phase, if a patient stopped taking treatment before their CRF Visit 3 (start of the stable dose) for a reason other than AE and then re-started study treatment more than 14 days after the treatment interruption, the analysis visit window for post-baseline visits will be derived using (as Day 1) the date the patient re-started their study treatment (i.e., the visit window will not be based on date of first dose for that patient).

Table 5: Visit Window and Target Day

Phase	Protocol Visit	Analysis Visit	Target Day	Visit Window Lower Limit	Visit Window Upper Limit
Safety: Vital Signs (including Height and Weight), Physical Examination, Clinical Laboratory, 12-lead ECG Efficacy: ESS-CHAD (parent/caregiver version), CaGI-S, CGI-S					
Screening	Visit 1 Visit 2	Baseline	-1	- inf	1
	Visit 3	Visit 3 (Day 22)	22	2	35
Daubla	Visit 4	Visit 4 (Day 50)	50	36	63
Double- Blind	Visit 5	Visit 5 (Day 77)	77	64	Treatment Phase Completion ^a
OLE	Visit 6	Visit 6 (Month 4)	99		-
	Visit 7	Visit 7 (Month 6)	189		

Dhasa	Protocol	Analysis Visit	Tayget Day	Visit Window	Visit Window
Phase	Visit		Target Day	Lower Limit	Upper Limit
	Visit 8	Visit 8 (Month 9)	279		
	Visit 9	Visit 9 (Month 12)	369		
Visit x		Visit x (Month y) ^b	Previous visit target day + 180		
Efficacy: G	hrelin meas	urements			
Screening	Visit 2	Baseline	-1	- inf	1
Double- Blind	Visit 5	Visit 5 (Day 77)	77	2	+ inf
Efficacy: C	ogstate		-		•
Screening	Visit 1	Baseline	-1	- inf	1
Screening	Visit 2	Dascinic		- 1111	
	Visit 4	Visit 4 (Day 50)	50	36	63
Double- Blind	Visit 5	Visit 5 (Day 77)	77	64	Treatment Phase Completion ^a
	Visit 6	Visit 6 (Month 4) ^c	99		
OL E	Visit 7	Visit 7 (Month 6)	189		
OLE	Visit 8	Visit 8 (Month 9)	279		
	Visit 9	Visit 9 (Month 12)	369		
Efficacy: A	BC-2, MER	S-PWS ^c , ZBI-22, HQ-0	CT and FSZQ		
Screening	Visit 1 Visit 2	Baseline	-1	- inf	1
	Visit 3	Visit 3 (Day 22)	22	2	35
	Visit 4	Visit 4 (Day 50)	50	36	63
Double- Blind	Visit 5	Visit 5 (Day 77)	77	64	Treatment Phase Completion
OLE	Visit 6	Visit 6 (Month 4)	99		
	Visit 7	Visit 7 (Month 6)	189		
OLE	Visit 8	Visit 8 (Month 9)	279		
	Visit 9	Visit 9 (Month 12)	369		
PK					

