12.4.1.2 Missing Data Imputations

No explicit imputation will be performed for the primary analysis; however, the MMRM model will yield unbiased results under the assumption that data are missing at random.

A sensitivity analysis for the primary endpoint (change from Baseline in mean ESS-CHAD [parent/caregiver version] score) will be performed using a hypothetical strategy. In this approach,

the unobserved data following discontinuation for lack of efficacy or AEs will be assumed to follow the placebo distribution at the matching visit, conditioned on the patient's observed data (including Baseline). Missing data after a patient discontinues treatment (for reasons other than lack of efficacy and AE) and intermittent missing data will be assumed to be missing at random. Details for the imputation are provided in this section.

Patients who discontinue early from the Double-Blind Treatment Phase study drug will be asked to return to the clinic for an Early Termination (ET) visit for completion of assessments (schedule of assessments in Appendix 7). The ESS-CHAD (parent/caregiver version) score collected at ET visit will be mapped to be closest analysis visit based on the rules defined in section 9.2. A multiple imputation approach will be utilized for missing data at Visit 3 (Day 22), Visit 4 (Day 50) and Visit 5 (Day 77, Week 11).

Table 7 represents the imputation rules for the primary endpoint sensitivity analysis. Missing data will be imputed using a three-stage multiple imputation (MI) approach.

Table 7: Post-Baseline Values Scenario and Imputation Methods

Study Medication	Analysis Visit			Imputation	
Status	Visit 3	Visit 4	Visit 5	Imputation	
	Present	Missing	Present	Intermittent missing data will be imputed within	
Completed/ Discontinued	Missing	Present	Present	treatment group using MI under a missing at random assumption with observed values at all	
	Missing	Missing	Present	available time points (including Baseline).	
Discontinued	Present	Present	Missing	Missing data after the discontinuation will be	
due to lack of efficacy or due	Present	Missing	Missing	imputed within the Placebo group (regardless of their assigned treatment group) using MI approach with observed values at all available	
to AE	Missing	Missing	Missing	time points (including Baseline).	

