12.4.1.4.1 Caregiver Global Impression of Severity (CaGI-S)

CaGI-S for EDS is a Likert rating scale completed by the parent/caregiver to assess the likelihood of the patient falling asleep during daytime activities with the following possible responses:

Early Termination visits will be summarized under Visit 3, Visit 4, or Visit 5 (depending on the visit they are closest to, per section 9.2) regardless of the discontinuation reason.

Frequency count and percentage of patients for each category and by visit will be provided as well as shift from Baseline. In addition, the number and percentage of patients with at least one-point improvement from Baseline (responder) will be summarized by treatment group and active groups combined. Percentages will be based on the number of patients with non-missing CaGI-S at Baseline and at each post-baseline visit.

The change from Baseline will be analyzed using a MMRM approach. Fixed effects will be included for treatment, visit, treatment*visit interaction and, Baseline value. An unstructured covariance structure will be utilized; in the case of convergence issues, the same approaches as defined in section 12.4.1.4.3 will be followed; Kenward-Rogers degrees of freedom will be used. LS means, SE, and the LS mean differences (each treatment versus placebo and the pooled active groups versus placebo) at each visit will be reported. All estimates will be generated from a single model, i.e., the pooled estimates will be created via model contrasts.

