12.4.1.4.2 Clinical Global Impression of Severity (CGI-S)

From protocol version 1 to protocol version 3, CGI-S for overall impression of severity was a Likert-type rating scale completed by the investigator to assess the patient's condition, with the following possible responses:

From protocol version 4, CGI-S for overall impression of severity is a tikert-type rating scale completed by the investigator to assess the patient's condition, with the following possible responses:

For the reporting results from the Likert-type rating scale will be mapped to the Likert-type rating scale as shown in Table 9.

Table 9: Mapping from Likert-type Rating Scale to Likert-type Rating Scale

Likert-type Rating	Likert-type Rating

The same summaries and analysis as performed for CaGI-S will be repeated for the CGI-S endpoint. Further details on the inferential analysis are provided in section 12.4.1.5.1.

In addition, the number and percentage of patients with at least one-point improvement from Baseline (responder) will be summarized by treatment group and active groups combined. Percentages will be based on the number of patients with non-missing CGI-S at Baseline and at each post-baseline visit.

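### Week 11 responder percentages generally omit patients who stop before Day 64, so they can be inflated if those patients are mostly non-responders, and no missing-data check covers them

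*SAP*

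**What the plan says.** The SAP sets an observed-case denominator for all three responder summaries:

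- ESS-CHAD (12.4.1.3.3): "Percentages will be based on the number of patients with non-missing ESS-CHAD (parent/caregiver version) at Baseline and at each post-baseline visit". Patients at or below a Baseline score that is redacted are left out of this summary.
- CaGI-S (12.4.1.4.1): "Percentages will be based on the number of patients with non-missing CaGI-S at Baseline and at each post-baseline visit".
- CGI-S (12.4.1.4.2): "Percentages will be based on the number of patients with non-missing CGI-S at Baseline and at each post-baseline visit".

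I read this visit by visit: a patient counts at a visit if both Baseline and that visit are present.

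Data from patients who stop early are not discarded. The protocol's double-blind Schedule of Assessments says "Patients who prematurely discontinue study drug are required to complete the ET Visit", and Protocol 7.3.3 makes the ET evaluations the same as those at Visit 5, so all three scales are included. SAP 12.4.1.3.3 adds that "Early Termination visits will be summarized under Visit 3, Visit 4 or Visit 5", whichever is closest and whatever the reason for stopping. SAP 12.4.1.4.1 repeats this for CaGI-S, and CGI-S takes the same summaries as CaGI-S. Placement follows SAP 9.2.1, where "the endpoints will be analyzed and reported using the analysis visits as determined by the windowing". Table 5 gives Visit 3 as Days 2 to 35, Visit 4 as Days 36 to 63, and Visit 5 as Day 64 to the end of the treatment phase.

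On missing data, SAP 12.4.1.2 says: "A sensitivity analysis for the primary endpoint (change from Baseline in mean ESS-CHAD [parent/caregiver version] score) will be performed using a hypothetical strategy". That analysis gives placebo-based values to patients who discontinued for lack of efficacy or an AE. The SAP text contains no non-responder rule and no sensitivity analysis for the responder percentages.

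**The concern.** A percentage computed only on patients still observed is a fair description of the arm only if those who left would have responded about as often as those who stayed. Patients who stop for lack of efficacy are the obvious counter-example. If one arm loses more such patients before Day 64, its Week 11 responder rate rises relative to the other arm with no difference in effect.

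The stakes are modest. SAP 12.0 states that the study is meant to inform the design of later studies and that the relative strength of all measures is of interest, so descriptive tables will be read. ESS-CHAD responder status at Visit 5 also splits the exposure-response panels in SAP 12.4.1.6.6, and the same categorical summaries are repeated in the open-label extension (SAP 12.4.2). With 20 patients per arm, each missing patient moves the percentage visibly.

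**Working it through.** **Inputs.** From the documents: 20 patients per arm (Protocol 9.2, "The sample size is 60 patients (20 in the lower dose pitolisant group", with 20 in each other group) and the Table 5 windows. Assumed, because the documents give neither a dropout nor a responder rate:

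- R, the response rate if all 20 were observed at Visit 5
- d, the number missing at Visit 5
- q, the response rate that those missing patients would have had

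I also assume that all 20 are in the mITT population and meet the Baseline-score condition.

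**The plan's own figure.** There is no planned responder figure to reproduce. The sample-size statement that supplies the 20 per arm does reproduce. With SD 5, a difference of 3.9, 40 against 20 patients and a two-sided 0.05 level (assumed; the level is not legible in the SAP), power is 80.0% by the noncentral t on 58 df. The half-widths are 1.96 × 5 × √(1/20 + 1/40) = 2.68 and, with SD 6, 3.22, against the stated 2.7 and 3.2.

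**Step 1. Who leaves the Week 11 denominator.**

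| Day of ET score | Counts at | In Week 11 denominator |
|---|---|---|
| 2 to 35 | Visit 3 | generally no |
| 36 to 63 | Visit 4 | generally no |
| 64 or later | Visit 5 | yes |

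It is generally no because the schedule provides only safety calls after ET, and those do not collect the three scales. A patient who moves early into the extension has the Visit 5 window closed at the first open-label dose (Table 5, footnote a).

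**Step 2. Formula.** Observed-case rate = (20R − dq)/(20 − d). Its distance from R is d(R − q)/(20 − d), so the direction depends only on whether q is below, equal to or above R.

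**Step 3. Values for R = 40%** (20R = 8):

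| d | q = 0 | q = 20% | q = 40% | q = 60% |
|---|---|---|---|---|
| 2 | 44.4% | 42.2% | 40.0% | 37.8% |
| 4 | 50.0% | 45.0% | 40.0% | 35.0% |
| 6 | 57.1% | 48.6% | 40.0% | 31.4% |

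**Step 4. Two arms, same true rate.** With R = 40% and q = 0 in both: active with 4 missing, 8/16 = 50.0%; placebo with 1 missing, 8/19 = 42.1%. The apparent difference is 7.9 points. Over a fixed denominator both arms are 8/20 = 40.0%, a difference of 0.

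**Step 5. Relation to missing counted as non-response.** That rate is (20R − dq)/20, so the observed-case figure exceeds it by the factor 20/(20 − d): 1.05, 1.11, 1.25 and 1.43 for d = 1, 2, 4 and 6. The fixed-denominator rate equals R only when q = 0; otherwise it is low by dq/20. With d = 4 and q = 40% it gives (8 − 1.6)/20 = 32%, against a true 40%.

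**The case against.** A reader might infer three stronger points. The documents support none of them.

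- *An arm with more discontinuations will show a higher responder rate.* This needs the missing patients to be less likely responders. That is plausible for lack of efficacy, but patients who stop for an AE may have improved on sleepiness. Step 3 shows that the figure can move either way.
- *Everyone who stops for an AE or lack of efficacy is dropped.* ET scores are kept. Leavers assessed on Day 64 or later stay at Visit 5, and earlier ones count at Visit 3 or 4.
- *The plan contradicts itself by imputing such patients in one place and omitting them in another.* The placebo-based imputation is specified only for the primary mean change, as a sensitivity analysis against a missing-at-random primary analysis. It has not been extended to the responder tables, which is a gap and not a contradiction. Placebo-like outcomes are also not the same as non-response.

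The other side has further arguments. The responder percentages are descriptive, carry no test and are absent from the ordered endpoint list in SAP 12.4.1.1. Counts accompany the percentages and discontinuation reasons are tabulated (SAP 12.1.1), so a reader could roughly rebuild a fixed-denominator rate. The table shells, held separately, may already show numbers missing. The illustrated gap is also small against chance: the standard error of 8/16 minus 8/19 is √(0.25/16 + 0.421 × 0.579/19) = 16.9 points. Counting every missing value as failure would also penalise an ESS-CHAD score lost to one unanswered item.

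These arguments stand as limits on the point's weight, and they are reasons to keep the observed-case figure. They do not remove the gap: the SAP text fixes the denominator and plans no check on it.

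**Conclusion.** The point holds in conditional form. The Week 11 responder percentages for ESS-CHAD, CaGI-S and CGI-S generally exclude patients whose last assessment falls before Day 64, and nothing in the SAP tests the effect. They can be inflated, and differently by arm, if early leavers are mostly non-responders. The illustrated 7.9 points rests on assumed values (a 40% true rate, 4 against 1 missing, no responders among the missing) and predicts nothing about this trial. The primary MMRM and its sensitivity analysis do not use this denominator. This is a low-cost improvement to descriptive tables and leaves the main efficacy conclusions untouched.

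**What to change.** Keep the observed-case percentages. Beside them, in SAP 12.4.1.3.3, 12.4.1.4.1 and 12.4.1.4.2, add a Week 11 responder percentage whose denominator is all mITT patients with a non-missing Baseline (for ESS-CHAD, those meeting the existing Baseline-score condition). Count a missing Visit 5 value as non-response, at least after discontinuation for lack of efficacy or an AE, and state which rule applies. Show the number missing by arm and visit.

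The cost is one extra column in three descriptive tables, with no new data and no change to the primary analysis. The downside is a conservative rate: it will be too low where values are missing for reasons unrelated to response. That is why the new figure should sit beside the observed-case one and not replace it. Because the mITT population already requires some post-baseline assessment, any treated patient without one stays outside both figures and should be visible in the disposition table.

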After completing the Screening Period, eligible patients will be enrolled into the Double-Blind Treatment Phase of the study.

The Double-Blind Treatment Phase of the study will be 11 weeks, which includes a 3-week Titration Period and an 8-week Stable Dose Period. Eligible patients will be randomized in a 1:1:1 ratio to receive treatment with lower dose pitolisant, higher dose pitolisant, or matching placebo (20 patients per treatment group, ages 6 to 65 years). The lower and higher pitolisant doses, respectively in each age group, will be 8.9 mg and 17.8 mg for children ages 6 to <12 years, 13.35 mg and 26.7 mg for adolescents ages 12 to <18 years, and 17.8 mg and 35.6 mg for adults ages 18 to 65 years. In the Double-Blind Treatment Phase, patients will be titrated to their randomized stable dose of study drug during the 3-week Titration Period. After completion of the 3-week Titration Period, patients will continue to take study drug at their randomized stable dose once daily in the morning upon wakening for an additional 8 weeks of blinded treatment (Stable Dose Period). The duration of the Double-Blind Treatment Phase will be 11 weeks. Patients and/or their caregiver will receive telephone calls (TCs) from the study site on Days 8 and 15 (±3 days) (TCs 1 and 2, respectively) during the 3-week Titration Period to assess for adverse events (AEs) and concomitant medication use, complete the Columbia-Suicide Severity Rating Scale (C-SSRS), and review/confirm titration of study drug. During the 8-week Stable Dose Period, patients will complete safety, efficacy, and PK assessments at the study site on Day 22 (Visit 3), Day 50 (Visit 4), and Day 77 (Visit 5) (window for Visits 3, 4, and 5 is ± 3 days), and patients and/or their caregiver will receive TCs from the study site on Days 29, 36, and 57 (±3 days; TCs 3, 4, and 5, respectively) to assess for AEs and concomitant medication use, complete the C-SSRS and Anxiety, Depression, and Mood Scale (ADAMS), and confirm study drug dose. Specific procedures and assessments for Screening (Visit 1), Visit 3, and Visit 4 may be conducted remotely as detailed in Section 6.6.

At the end of the Double-Blind Treatment Phase, eligible patients will be given the opportunity to enter an optional OLE Phase. If a patient does not enter the OLE Phase, the patient and/or their caregiver will receive Safety Follow-up TCs from the study site 15 days (±3 days) and 30 days (+3 days) after their final dose of blinded treatment.

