12.0 Statistical Methods

All analyses will use SAS version 9.4 or higher. The analysis shells for the tables, listings, and figures will be provided in a separate document.

Categorical variables will be summarized using counts and percentages based on the specified population total. Percentages will be rounded to one decimal place, except 100% will be displayed without any decimal places and percentages will not be displayed for zero counts.

Continuous data will be summarized using non-missing observations (n, mean, SD, median, minimum, and maximum). The median, minimum, and maximum values will be displayed to the same level of the precision as the raw value. Mean and median will be rounded to 1 decimal place greater than the precision of the original value. The SD will be rounded to 2 decimal places greater than the precision of the original value. Confidence intervals, least square (LS) means, and standard error (SE) will be provided as appropriate. Confidence intervals, LS means will present the same precision as the mean value whereas SEs will present the same precision as SD.

P-values will be rounded to 4 decimal places. P-values less than 0.0001 will be presented as "<0.0001" and p-values greater than 0.9999 will be presented as ">0.9999."

For safety laboratory parameter and ghrelin levels, results reported as "<xx" will be imputed to xx; and result reported as ">xx" will be imputed to xx.

Statistical hypothesis testing will be and carried out at the level of significance.

The study objective is to evaluate the effectiveness of pitolisant in treating EDS and other symptoms of PWS for the purposes of informing the design of future studies in patients with PWS, a rare pediatric neurodevelopmental disorder. As such, the relative strengths of all measures are of interest and p-values will be reported with no formal multiplicity adjustments.

All the listings will be displayed by treatment arm, patient identifier and date of assessment. Age, sex, and race will be presented.

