12.4.1.1 Hypothesis Testing Strategy

The study is a Phase 2 proof of concept and is not powered to show statistical significance; therefore, no formal multiplicity adjustment will be done.

All tests will be 2-sided. P-values will be reported for the individual doses, the combined doses, and for all the outcomes.

The following order reflects the endpoints of most interest and greater consideration will be given to successful endpoints higher in the list, particularly when all preceding endpoints have a significant p-value. For the secondary endpoints, interpretation of the results regarding statistical significance will be based on the pattern of results.

Primary Endpoint:

- Change in mean ESS-CHAD (parent/caregiver version) score from Baseline to Week 11 (Visit 5) for the high dose group compared with placebo
- Change in mean ESS-CHAD (parent/caregiver version) score from Baseline to Week 11 (Visit 5) for the low dose group compared with placebo
- Change in mean ESS-CHAD (parent/caregiver version) score from Baseline to Week 11 (Visit 5) for the pooled active doses group compared with placebo

Key Secondary Endpoints:

- Change from Baseline to Week 11 (Visit 5) in Caregiver Global Impression of Severity (CaGI-S) for EDS for the high dose group compared with placebo
- Change from Baseline to Week 11 (Visit 5) in Clinician Global Impression of Severity (CGI-S) for overall clinical status related to PWS for the high dose group compared with placebo
- Change from Baseline to Week 11 (Visit 5) in CaGI-S for EDS for the low dose group compared with placebo
- Change from Baseline to Week 11 (Visit 5) in CGI-S for overall clinical status related to PWS for the low dose group compared with placebo
- Change from Baseline to Week 11 (Visit 5) in CaGI-S for EDS for the pooled active doses group compared with placebo
- Change from Baseline to Week 11 (Visit 5) in CGI-S for overall clinical status related to PWS for the pooled active doses group compared with placebo

Other Secondary Endpoints:

• Change from Baseline to Week 11 (Visit 5) in behavior as measured by the Aberrant Behavior Checklist, Second Edition (ABC-2) for the high dose group compared with placebo

- Change from Baseline to Week 11 (Visit 5) in behavioral and cognitive rigidity as measured by the Montefiore-Einstein Rigidity Scale – Prader-Willi Syndrome (MERS-PWS) for the high dose group compared with placebo

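### The last convergence fallback drops Kenward-Roger for an uncorrected sandwich variance; if a small subgroup reaches it, type I error exceeds 5%, and the listed ANCOVA should come first

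*SAP*

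**What the plan says.** The default in SAP 12.4.1.3.3 is "An unstructured covariance structure will be utilized; Kenward-Rogers degrees of freedom will be used". If it does not converge, four steps follow in order: Fisher scoring, the FA0(T) structure, successive univariate regression, and last ARH(1) and then compound symmetry (CS) with a sandwich variance. At that last step, "for the sandwich variance estimator Kenward-Rogers degrees of freedom will be replaced by the EMPIRICAL option".

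SAP 12.4.1.6.5 repeats the list, with the same parenthesis, for the subgroup analyses by age group and by concomitant sleep disorder. It leaves out univariate regression, so the sandwich is step 3 of 3. The steps are applied in the listed order until one converges. A later sentence replaces the MMRM with an ANCOVA or a t-test when the sample is too small, and gives convergence problems as an example. Subgroup inference is run only above a size threshold, which is blacked out.

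Protocol 9.4.2.1.1 names AR(1) and CS as fallbacks, keeps Kenward-Roger and mentions no sandwich. SAP 6.1 records the change only as added detail on convergence.

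Two things are not explicit. The parenthesis can be read as covering CS only, or both ARH(1) and CS. The rank of the ANCOVA relative to the sandwich step is also not stated.

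**The concern.** The classical sandwich builds its variance from each patient's residuals. With few patients, each one pulls the fit towards itself, so the residuals are too small and the standard error is biased downward. Kenward-Roger is the plan's protection against small-sample error. The EMPIRICAL option removes it, and the text puts nothing in its place.

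The subgroup section is where this matters most, because its cells are smallest and it has one step fewer before the sandwich. Read literally, a sandwich model that converges pre-empts an ANCOVA that holds its level. If the order is instead left open, the analyst could choose between two tests after seeing the data. Either way, a subgroup result from this step could show too narrow an interval or a false signal, in a study meant to inform later designs.

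**Working it through.** **Inputs from the documents.** Size: "The sample size is 60 patients (20 in the lower dose pitolisant group, 20 in the higher dose pitolisant group", with 20 on placebo. Allocation: "Eligible patients will be randomized in a 1:1:1 ratio". Sidedness: "All tests will be 2-sided". Variability: "Prior research suggests that the ESS-CHAD SD falls between 5 to 6"; the overall SD cancels from the test, so this range does not affect type I error. Age groups: three (SAP 12.4.1.6.5). Randomization is not stratified by age (Protocol 3.1.2).

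**Assumptions.** Alpha is 0.05, because the SAP's sentence reads "Statistical hypothesis testing will be and carried out at the level of significance" with the value blacked out; the protocol's 95% intervals agree with 0.05. Within-patient correlation is 0.6 and dropout is 0% to 30%; the documents give neither.

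**1. The plan's own figures.** Protocol 9.2 says "the study would be powered at 80% to detect a difference of 3.9 between the pooled pitolisant groups and placebo group", with 95% half-widths of 2.7 (SD 5) and 3.2 (SD 6).
- 1.96 × 5 × √(1/20 + 1/40) = 2.68, and 1.96 × 6 × √(1/20 + 1/40) = 3.22.
- Power for 3.9 at SD 5, noncentral t with 58 df: 80.0%.

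Both reproduce. The documents state no type I error for the fallback.

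**2. Subgroup size.** 60 / (3 arms × 3 age groups) = 6.7, taken as 7 per arm.

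**3. Type I error once the sandwich step is used.** The null simulation used 6,000 trials per setting, with Monte Carlo standard error √(0.09 × 0.91 / 6000) = 0.4 points. The model had 3 arms, 3 visits, treatment, visit, their interaction and baseline. The working covariance was CS or ARH(1), with a classical sandwich. The test was high dose versus placebo at Visit 5. The SAP text does not say which reference distribution replaces Kenward-Roger, so three are shown.

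| Patients per arm | Within-subject df | Between-subject df | Normal |
|---|---|---|---|
| 7, complete data | 8.5% to 9.4% | 6.9% to 8.1% | 9.3% to 10.3% |
| 7, 15% dropout | 10.5% | 9.6% | 11.7% |
| 5/7/9 (uneven) | 10.2% to 10.5% | not listed | not listed |
| 5 | 11.5% | not listed | not listed |
| 10 | 7.3% to 7.9% | not listed | not listed |
| 20 (primary analysis) | 6.0% to 6.3% | not listed | not listed |

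A second set-up used 4,000 trials, SDs of 4.5, 5 and 5.5, correlations of 0.45 to 0.65, CS and within-subject df. It gave 5.8%, 9.2% and 12.6% at 20, 7 and 5 per arm.

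**4. How often the unstructured model fails (REML).**
- 7 per arm: 0/150 with complete data, 0/300 with 15% dropout, 5/300 = 1.7% with 30% dropout.
- 20 per arm: 0/60 with 15% dropout.
- 3 per arm: 92/300 = 31% with 25% dropout.

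**5. The procedure as a whole at 7 per arm.** Suppose the default test holds 5% and 2% of analyses go to the sandwich: 0.98 × 5% + 0.02 × 9% = 5.1%. This overstates the excess if Fisher scoring or FA0(T) rescues some of the failures.

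**6. Alternatives at 7 per arm.**
- ANCOVA at Visit 5: 4.3% to 5.7%.
- Bias-corrected (Mancl-DeRouen) sandwich with between-subject df: 3.4% to 4.8%.
- Model-based ARH(1) with between-subject df: 5.0% to 5.9%.
- Model-based CS: up to 9.7% when visit variances differ, so it is not a safe replacement.

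Kenward-Roger itself was not simulated.

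**The case against.** The strongest case against the point is that the step is almost never reached. At 7 per arm the unstructured model nearly always converged, and two rescue steps come before the sandwich. In the primary analysis a third, univariate regression, comes first; it needs no joint covariance fit, so reaching step 4 is improbable. The blacked-out size threshold may already exclude cells of 5 or 7 per arm. The ANCOVA sentence in SAP 12.4.1.6.5 can be read as the intended response to non-convergence. If the parenthesis covers CS only, ARH(1) already keeps Kenward-Roger. The sample code in SAP Appendix 4 is not shown and could fix the degrees of freedom.

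Most of this stands, and it limits the point. A reader might infer that the subgroup analyses run at about 9% type I error, or that the primary result is in doubt. The documents support neither. The 9% is conditional on the last step, the subgroup sizes are unknown, and the corresponding primary figure is about 6%.

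What remains is that the written text names no correction and no degrees of freedom, and lists the sandwich ahead of a test that holds its level. A fallback exists for the cases where the default fails, and those become more common as cells shrink.

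**Conclusion.** The point holds in conditional form and is minor. If the sandwich step produces a subgroup result, its two-sided type I error is roughly 7% to 12% at 7 per arm, depending on degrees of freedom, dropout and balance, and about 11% to 13% at 5 per arm. These figures rest on the alpha, age split, correlation and dropout assumed above, and on normally distributed outcomes. The one-item CaGI-S and CGI-S scales were not simulated. Severity stays low because the subgroup analyses sit under the exploratory analyses and no p-value in this proof-of-concept study is adjusted for multiplicity (SAP 12.4.1.1).

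**What to change.** In SAP 12.4.1.6.5, delete step 3 (ARH(1) and CS with sandwich and EMPIRICAL). State that if the first two steps fail, the analysis goes directly to the ANCOVA already listed, at Week 11 as in Protocol 9.4.2.1.3. This also settles the order.

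In SAP 12.4.1.3.3, step 4, state that ARH(1) keeps model-based standard errors with Kenward-Roger. For CS, name a small-sample bias-corrected sandwich with between-subject degrees of freedom.

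The cost is a few words and one procedure option. Intervals are slightly wider if the fallback is reached, and the ANCOVA uses only patients with Week 11 data.
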